3.6 SCHEDULE OF EVENTS

The schedule of study procedures and assessments is presented by visit in the Schedule of Events in [Table 2](#).

Table 2. Schedule of Events

	Screening Period (Up to 4 weeks)^w	Pretreatment Period (2 weeks)	Treatment Period (8 weeks)				Follow-up
Visit Days →	Screening Visit (Day -49 to Day -15)	Pretreatment Visit (Day -21 to Day -1)	Randomization Visit (Day 1)	Week 2 Visit (Day 15 ± 3)	Week 4 Visit (Day 29 ± 3)	Week 8 / End-of-treatment Visit (Day 57 ± 3)	EOT + 7 days
Visit Numbers →	Visit 1	Visit 2	Visit 3	Visit 4	Visit 5	Visit 6	
Study Procedure ↓							
Inclusion and Exclusion Criteria Verification	X	X	X				
Signing of ICF	X						
IWRS Registration (a)	X	X	X	X	X	X	
Medical History	X						
Demographics	X						
Physical Examination (b)	X						X
Body Weight and Height (c)	X	X	X	X	X	X	
H2RA/Antacid Washout (d)	X						
Bilitec Monitoring (e)	X						
EGD (f)	X						X
48 to 96 Hours of pH Testing with Bravo Device (g)	X						
Seated Vital Signs (h)	X	X	X	X	X	X	
12-Lead ECG (i)	X		X				X
Prior and Concomitant Medications (j)	X	X	X	X	X	X	
Clinical Laboratory Tests(k)	X		X		X	X	
Serum Pregnancy Test (l)	X						X
Urine Pregnancy Test (l)			X		X		

Table 2. Schedule of Events

	Screening Period (Up to 4 weeks) ^w	Pretreatment Period (2 weeks)	Treatment Period (8 weeks)				Follow-up
Visit Days →	Screening Visit (Day -49 to Day -15)	Pretreatment Visit (Day -21 to Day -1)	Randomization Visit (Day 1)	Week 2 Visit (Day 15 ± 3)	Week 4 Visit (Day 29 ± 3)	Week 8 / End-of-treatment Visit (Day 57 ± 3)	EOT + 7 days
Visit Numbers →	Visit 1	Visit 2	Visit 3	Visit 4	Visit 5	Visit 6	
Study Procedure ↓							
Drug and Alcohol Screen (m)	X						
AE Evaluations (n)	X	X	X	X	X	X	
Rescue Medicine Dispensed (o)		X	X	X	X		
PDA Training and Dispensation		X					
Saliva Collection (p)	X	X	X		X	X	
eDiary (q)		X	X	X	X	X	
Weekly Symptom and Treatment Assessments (r)		X	X	X	X	X	
GSRS-Self			X		X	X	
QIDS-SR-16			X				
SF-12V2			X		X	X	
EQ-5D-3L			X		X	X	
Randomization			X				
Study Medication Dispensed (s)			X	X	X		
Study Medication Return (t)				X	X	X	
PDA Return						X	
mRESQ Debrief Interview (x)		X (x)			X (x)		
End-of-treatment Question (u)						X	
Safety Follow-up Call (v)							X

Abbreviations: AE = adverse event; BP = blood pressure; CBC = complete blood count; ECG = electrocardiogram; EGD = esophagogastroduodenoscopy; EOT = End-of-treatment; EQ = EuroQol; GSRS = Gastrointestinal Symptoms Rating Scale; H2RA = histamine-2 receptor antagonist; HEENT = head, eyes, ears, nose, and throat; ICF = informed consent form; IWRS = interactive web response system; PDA = personal digital assistant; PPI = proton pump inhibitor; QID = Quick Inventory of Depressive Symptomatology; mRESQ-eD = modified Reflux Symptom Questionnaire Electronic Diary; SAE = serious adverse event; SF = short form

- a. Site personnel will interact with IWRS to register the patient visit and transition the patient to the next appropriate study period.
- b. A physical examination should include the following assessments: general appearance; HEENT; neck; cardiovascular; respiratory; abdomen/liver/spleen; musculoskeletal; lymph nodes; skin; neurologic; nervous system, and mental status. Breast, genitourinary, and rectal examinations are optional and may be performed at the discretion of the Investigator.
- c. Height will be measured only at the Screening Visit.
- d. During the Screening Period, patients will begin to washout H2RAs and antacids. H2RAs should be stopped 5 calendar days prior to the EGD and Bravo pH monitoring and antacids should be stopped 1 calendar day prior to the EGD and Bravo pH monitoring. Patients may resume antacid use upon completion of the Bravo testing, but must refrain from H2RA use for the remainder of the study. During the Pretreatment Period, patients will refrain from using any anti-reflux medications, antacids, and H2RAs, except for the antacids that are provided as rescue medicine). Patients will continue to use their current PPI during the Pretreatment Period.
- e. At selected sites, selected patients who are screened for the study with EGD and Bravo testing will also be given the option of having a Bilitec monitor inserted during the same procedure. These patients will return 24 hours later for removal of the probe. The results of the Bilitec test will not affect qualification for enrollment. The Bilitec device and Bravo recorder internal clocks must be synchronized, and both devices should be activated concurrently; however, if it is not possible to simultaneously activate both devices, the Bravo recorder should be activated first, with the Bilitec device activated immediately (within 5 minutes) after the Bravo pH recorder activation.
- f. All patients will be required to undergo an EGD during the Screening Period. There must be a minimum of 7 days between the EGD and the start of the Pretreatment Period. An EGD will be performed at the Week 8/EOT Visit in all patients who have Grade C or D esophagitis (based on the Los Angeles classification of esophagitis; see [Appendix 5](#)) on the EGD obtained during the Screening Period.
- g. Approximately 48 to 96 hours of pH testing with the Bravo device. If for some reason 96 hours of testing is not possible, then approximately 48 hours of testing is acceptable. During the entire period of Bravo pH monitoring (approximately 48-96 hours), patients will record ingestion of all meals, snacks, and drinks by depressing the 'meal' button on the Bravo recorder upon the beginning and completion of the meal, snack, or drink. Patients will also record any periods during which they are lying down by depressing the 'supine' button on the Bravo recorder at the beginning and upon completion of the supine period. In addition, for the entire 48-96 hour Bravo pH monitoring period, patients will also complete a paper diary (see [Appendix 9](#)), recording at a minimum, all instances of meals, snacks, drinks, and/or resting in the supine position.
- h. Vital sign measurements include oral temperature (°C), respiratory rate, systolic and diastolic BP, and pulse. Respiratory rate, BP, and pulse measurements must be obtained after the patient has been seated for at least 5 minutes.
- i. 12-lead ECGs should be obtained after the patient has been supine for at least 5 minutes.
- j. Prior medications will be collected at the Screening Visit as follows: all medicines taken by the patient during the 30 days before the Screening Visit, most recent use of an H2RA, and most recent use of an antacid.
- k. Clinical laboratory tests include clinical chemistry, hematology (CBC), coagulation, and urinalysis. If the triglyceride value exceeds the protocol-specified criteria and the patient was not under fasted conditions, the patient may return to completed a fasted lipid panel.
- l. For all female patients of childbearing potential, a negative serum pregnancy test must be documented at the Screening Visit, and a negative urine pregnancy test must be documented at the Randomization Visit (before dosing) in order for the patient to be randomized into the study. A urine pregnancy test will be obtained at the Week 4 Visit; serum pregnancy test will be conducted at the EOT Visit.

- m. Patients must undergo a urine drug screen for selected drugs of abuse (cocaine, barbiturates, amphetamines, opiates, benzodiazepines, and cannabinoids) and a serum alcohol screen at the Screening Visit.
- n. All AEs will be captured from the time the patient signs the ICF through the EOT Visit.
- o. Rescue medicine will be supplied to patients at the Pretreatment Visit, and if needed, at subsequent visits.
- p. At each of the indicated visits, patients will provide approximately 1 mL of saliva for future use (bile acids will be quantified in the saliva, and the quantity of bile acid may be used to define potential responders to IW-3718). At the time of saliva collection, study site staff will collect the following information: time of day, time of patient's last meal, and time of last study medication administration. During the Randomization Visit, study site staff will collect the saliva sample immediately following the light snack but prior to study drug administration.
- q. The eDiary will be dispensed at the Pretreatment Visit and patients must complete 5 days each week during the 14 calendar days before the Treatment Period in order to be eligible for randomization. Patients should bring their eDiary to each visit. The eDiary will collect daily PPI administration, rescue medication use, mRESQ-eD ([Appendix 1](#); daily), Daily Assessment of Sleep ([Appendix 3](#); daily), Daily Dyspepsia Symptoms ([Appendix 2](#); daily).
- r. Symptom bothersomeness and relief items ([Appendix 6](#); weekly); Treatment satisfaction item ([Appendix 6](#); weekly).
- s. The first dose of study medication will be administered in the clinic with liquid and a snack at the Randomization Visit. At all other visits, patients will take their study medication prior to arriving at the clinic, but will be dispensed additional doses needed until the next study visit.
- t. Treatment compliance with study drug will be assessed based on return of unused tablets.
- u. All patients will be asked an EOT question regarding the difficulty of swallowing the IW-3718 or placebo tablets ([Appendix 6](#)).
- v. Study site will contact each patient via telephone 7 days after the EOT Visit to collect information pertaining to ongoing AEs/SAEs and information concerning any new AEs/SAEs since the EOT Visit
- w. Ironwood may grant a one-week extension of the screening period window if needed for logistical delays (e.g., subject travel, scheduling issues, delays in test results, equipment malfunction, etc.). Approval should be requested from Ironwood prior to each extension.
- x. Patients participating in the optional mRESQ-eD Cognitive Debriefing interviews will be assigned to one of three interview groups. Interviews will take place at different timepoints depending on the patient's group assignment. (see [Appendix 10](#))

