- GERD symptoms assessed once daily in the evening in the modified Reflux Symptom Questionnaire eDiary (mRESQ-eD; [Appendix 1](#))
- Dyspepsia symptoms assessed once daily in the evening using Daily Dyspepsia Symptoms ([Appendix 2](#))
- Assessment of sleep assessed once daily in the morning using Daily Assessment of Sleep ([Appendix 3](#))
- Use of per-protocol rescue medicine assessed twice daily
- Symptom relief and bothersomeness assessed once a week in the evening

Patients will be instructed to take their PPI at least approximately 30-60 minutes before breakfast each day, even on study visit days. Patients who satisfy all of the entry criteria will enter the Treatment Period.

Treatment Period: The Treatment Period begins with treatment assignment and lasts for 8 weeks. Patients will be stratified by whether they have, or do not have, erosive esophagitis on the screening EGD and randomly assigned to 1 of 4 treatments (1:1:1:1) within each stratum: placebo or 500 mg IW-3718 BID, 1000 mg IW-3718 BID, or 1500 mg IW-3718 BID. The treatment schedule will be managed by a central vendor. Enrollment will be monitored to ensure that no single center contributes > 15% of the targeted study enrollment, unless otherwise approved by the Medical Monitor. Study drug will be taken immediately after the morning and evening meals. Patients will continue to take their PPI approximately 30-60 minutes before breakfast each day and to use the eDiary to provide their daily assessments (GERD symptoms, dyspepsia symptoms, assessment of sleep), weekly assessments (weekly symptom

bothersomeness and degree of relief questions; [Appendix 6](#)), PPI compliance, and use of per-protocol rescue medicine.

For details regarding the assessments during each study period, see the Schedule of Events ([Table 2](#)).

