3.3.2 Removal of Patients from Therapy or Assessment

A premature discontinuation will occur when a patient who has signed the ICF ceases participation in the study, regardless of circumstances, before completion of the Treatment Period.

A patient will be considered to have completed the study after receiving 8 weeks of treatment and completing the End-of-treatment (EOT) Visit at Day 57. A window of +3 days will be allowed for the EOT visit; if a patient completes the EOT Visit prior to Day 57, this will be considered a protocol deviation.

Patients will be informed that they are free to withdraw from the study at any time and for any reason. The Investigator may remove a patient from the study if, in the Investigator's opinion, it is not in the best interest of the patient to continue the study. Patients may also be discontinued from the study by the Investigator or the Sponsor at any time for any reason, including the following:

- Failure to meet an inclusion/exclusion criterion that is clinically relevant and affects patient safety
- Adverse event(s)

- Protocol violation, including lack of compliance
- Insufficient therapeutic response (lack of efficacy)
- Lost to follow-up (every effort must be made to contact the patient; a certified letter must be sent)
- Withdrawal of consent (attempts should be made to determine the reason for the patient withdrawing consent if possible)
- Study termination by the Sponsor
- Other reasons (e.g., administrative reasons or pregnancy)

The date the patient is withdrawn from the study and the reason for discontinuation will be recorded on the study termination form of the electronic case report form (eCRF). Patients who discontinue from the study for any reason should complete the assessments required at the EOT Visit at the time of their discontinuation. Patients who discontinue from the study will be followed until resolution of all of their AEs or until the unresolved AEs are judged by the Investigator to have stabilized. Study centers should make a reasonable effort to follow any pregnant patients until delivery or end of the pregnancy.

If a patient does not return for a scheduled visit, the study center should contact the patient. An effort must be made to contact the patient, including sending a certified letter. In every case, the patient outcome, including lost to follow-up information, will be documented.

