3.4.6 Selection and Timing of Dose for Each Patient

Patients will be randomized to receive 500 mg IW-3718 BID, 1000 mg IW-3718 BID, 1500 mg IW-3718 BID, or placebo BID. The first dose of study medication will be taken with liquid and a snack in clinic at the Randomization Visit (on Day 1). Patients should take their second dose that evening immediately upon completion of dinner, ensuring that at least 8 hours have elapsed since the first dose in clinic.

During the Treatment Period, patients will take study medication BID at home, in the morning (immediately upon completion of breakfast) and in the evening (immediately upon completion of dinner), even on study visit days. The last dose of study medication will be taken the morning of the EOT Visit.

Additionally, all patients will take their current PPI during the Pretreatment, Randomization, and Treatment Periods (i.e., Day -21 through Day 57 [+ 3 days]). The PPI will be taken each day, approximately 30-60 minutes before breakfast.

During completion of the PDA daily diary questions, patients will be asked to confirm daily dosing of their PPI by responding to the following question:

- “Did you take your PPI this morning?”

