3.5 SAFETY AND EFFICACY ASSESSMENTS

The timing of safety and efficacy assessments is presented in Section [3.6](#).

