3.6.2 Treatment Period (Day 1 to Day 57)

For all visits during the Treatment Period, patients will take their PPI and study medication (except for the Randomization Visit) prior to reporting to the study site.

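### Protocol Table 2 sets the Week 8/EOT visit at Day 57 ± 3, but section 3.3.2 allows + 3 only; a visit on Days 54 to 56 cuts short the primary endpoint week

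*Protocol*

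**What the plan says.** The protocol gives two different windows for the Week 8/EOT visit.

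- **Section 3.6, Table 2.** Both header blocks give "Week 8 / End-of-treatment Visit (Day 57 ± 3", that is, Days 54 to 60.
- **Section 3.3.2.** "A window of +3 days will be allowed for the EOT visit", that is, Days 57 to 60. It adds: "if a patient completes the EOT Visit prior to Day 57, this will be considered a protocol deviation". The same section ties study completion to 8 weeks of treatment and the EOT visit at Day 57.

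The other places that bear on the window agree with section 3.3.2:

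- Section 3.4.6 has the PPI taken over "Day -21 through Day 57 [+ 3 days".
- The synopsis Schedule of Events and SAP Table 4.4-1 both print Day 57 + 3.
- The heading of section 3.6.2 is "Treatment Period (Day 1 to Day 57".

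Table 2 is nonetheless where the body of the protocol sends its reader. Section 3.1 says "For details regarding the assessments during each study period, see the Schedule of Events" and names Table 2. Section 3.5 opens with "The timing of safety and efficacy assessments is presented in Section" and points to 3.6.

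**The concern.** A site that books from Table 2 can, in good faith, bring a patient in on Day 54, 55 or 56. Under section 3.3.2 that visit is a deviation, and it is unclear whether the patient counts as a completer.

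The early visit also shortens treatment and cuts into the week that defines the primary endpoint. Four rules combine to do this:

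- Week 8 is Days 50 to 56 (Protocol Table 3, SAP Table 5.10-1).
- The heartburn items are entered at bedtime (Protocol 3.5.2.1.1, SAP 4.1.1.1).
- On the EOT visit day the SAP expects the morning diary only (SAP 5.9), and the diary device is handed back (Protocol 3.6.2.4).
- "The last dose of study medication will be taken the morning of the EOT Visit" (Protocol 3.4.6).

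At stake is avoidable loss of primary-week data in individual patients, together with deviations that the protocol's own visit table invites.

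**Working it through.** **Permitted visit days**

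- Table 2: Days 54 to 60 = 7 days.
- Section 3.3.2: Days 57 to 60 = 4 days.
- Difference: Days 54, 55 and 56. So 3 of the 7 days allowed by Table 2 are deviations under section 3.3.2.

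**Evening scores available for Week 8**

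A daily heartburn score for day *d* (50 to 56) can exist only if *d* is before the visit day *V*. For *V* from 54 to 57 the maximum number of scores is therefore *V* − 50. From Day 57 onward it is 7.

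**Scheduled doses**

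There are two doses on Day 1 and on each later day up to the day before the visit, then one on the morning of the visit: doses = 2(*V* − 1) + 1. For Day 57 this is 2 × 56 + 1 = 113. The compliance formula in SAP 5.6 gives the same number: 57 × 6 − 3 = 339 tablets, and at 3 tablets per dose 339 / 3 = 113.

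| EOT visit day | Week 8 scores possible | Share of 7 | Scheduled doses | Omitted, of 113 |
|---|---|---|---|---|
| 54 | 4 | 57% | 2 × 53 + 1 = 107 | 6 (5.3%) |
| 55 | 5 | 71% | 2 × 54 + 1 = 109 | 4 (3.5%) |
| 56 | 6 | 86% | 2 × 55 + 1 = 111 | 2 (1.8%) |
| 57 | 7 | 100% | 113 | 0 |
| 58 to 60 | 7 | 100% | more than 113 | 0 |

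**What the analysis rules do with the loss**

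- SAP 5.10.1 averages the available daily scores and sets no minimum, so a Week 8 WHSS is still obtained from 4, 5 or 6 days.
- SAP 5.10 classes a patient with 4 or more missed days as a non-responder for the week. An early visit alone removes at most 3 days, so it does not trigger the rule. After a Day 54 visit, however, one further missed evening would (3 + 1 = 4).

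**The case against.** The strongest reply is that the protocol already states the right rule. Section 3.3.2 gives the window and the consequence of breaching it, and the synopsis schedule, section 3.4.6 and the SAP schedule agree. A specific sentence should prevail over a table header. This shows which rule was intended, and it is a main reason the point is minor. It does not remove the conflicting window from the table that sections 3.1 and 3.5 direct readers to.

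A second reply is that the difference is one character, which could be a misreading in the conversion of the PDF to text. Table 2 shows other signs of poor conversion: the final marks for physical examination, EGD, ECG and serum pregnancy test fall in the follow-up column, although section 3.6.2.4 places them at the EOT visit. A misread sign therefore cannot be excluded. It is unlikely, though, because the synopsis schedule has the same column shift and still shows ± for Weeks 2 and 4 and + for Week 8 in one header row. The text description of the synopsis design diagram also reads ± 3. The diagram itself could not be seen, so it carries no weight here.

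A third reply is that the harm is hypothetical: a site must follow the header, overlook section 3.3.2 and book early. That is correct. The documents give no frequency of early visits, and the figures above apply only to a patient who is booked early.

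**Conclusion.** The inconsistency is real, and + 3 is the intended and sound window. Table 2 is wrong as written.

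The finding is minor. For a patient seen on Days 54 to 56, the Week 8 score loses 1 to 3 of its 7 evening entries, and 2 to 6 of the 113 scheduled doses are omitted. The endpoint remains computable. Nothing suggests that early visits would differ by arm, and no trial-level effect can be estimated.

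The conclusion assumes that the ± in Table 2 is printed as read. The counts also assume that no evening entry is made on or after the EOT visit day, as SAP 5.9 and the return of the device at that visit imply.

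**What to change.** Change ± 3 to + 3 for the Week 8/EOT visit in both header blocks of Protocol Table 2. Check the design figure and correct it if it shows ± 3. Every permitted visit day then allows all 7 Week 8 evening scores to be collected.

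An administrative amendment or a clarification letter to sites is enough. The design, sample size and SAP do not change.

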3.6.1 Screening Period (Day -49 to Day -15)

3.6.1.1 Screening Visit (Visit 1) Procedures

- Signing of ICF
- Register visit in IWRS
- Review of inclusion and exclusion criteria
- Demographics
- Medical history
- Physical examination
- Body weight and height
- Begin H2RA and antacid washout (for 5 calendar days before the EGD and Bravo pH monitoring [H2RA] and 1 calendar day before the EGD and Bravo pH monitoring [antacids])
- EGD
- Approximately 48 to 96 hours of pH testing with a Bravo device (if 96 hours of testing is not possible, then approximately 48 hours of testing is acceptable)
- Optional 24 hours of measurements of bilirubin using the Bilitec device (for patients undergoing the Bilitec procedure – device removed after 24 hours)
- Seated vital signs
- 12-lead ECG
- Prior medications (all medicines taken during the 30 days before the Screening Visit, most recent use of an H2RA, and most recent use of an antacid)
- Collection of blood and urine samples for clinical laboratory test, including:
 - Clinical chemistry
 - Hematology (complete blood count [CBC])
 - Coagulation
 - Urinalysis
- Serum pregnancy test for all female patients of childbearing potential (must be confirmed negative)
- AE evaluation (throughout the Screening Period)
- Saliva collection

3.6.1.2 Extension of Screening Period

Ironwood may grant a one-week extension of the screening period window if needed for logistical delays (e.g., subject travel, scheduling issues, delays in test results, equipment malfunction, etc.). Approval should be requested from Ironwood prior to each extension.

If an extension of greater than one week is needed for logistical delays, subjects will be considered screen failures and will need to re-screen. If these subjects had already completed the EGD/Bravo (and Bilitec, if applicable) assessments during the original screening period, they will not need to repeat these tests as long as they enter Pre-Treatment within 35 days of the assessments. All other study assessments should be repeated during re-screening. Pretreatment Period (Day -21 to Day -1).

